## 1. BACKGROUND

Since 2012, the asymmetric multifocal posterior chamber lens MICS LS-313 MF30 (Oculentis GmbH, Berlin, Germany) has been implanted in the Department of Ophthalmology Neubrandenburg following cataract surgery in suitable patients.

To determine the refraction after the implantation of an asymmetric multifocal intraocular lens we have used the eye refractometer PR 60 or PR 50 (Rodenstock, Munich). This manual refractometer projects test mark images onto the retina of the eye via a measuring beam path, which are viewed via a coaxial observation beam path and are manually focused.

So far, this is our only objective way to measure the different focal points of the multifocal lens.

Furthermore, we have the opportunity to determine the distance and near refraction subjectively. The accuracy of this method, however, depends on the cooperation of the patient.

The manual eye refractometers PR 60 and PR 50 (Rodenstock, Munich) work with light cones of 3 mm diameter.

The optic of the LS-313 MF30 intraocular lens has a diameter of 6 mm, half of the optic is used for far vision, half for near vision. Under ideal conditions (pupil becomes maximally dilated; no peripheral capsule opacity or secondary cataract cover the peripheral part of the optic) the Rodenstock refractometer provides a sharp image on the fundus.

However, usually it is not possible to image the entire light cone of the Rodenstock refractometer on the retina in case of a non-maximally dilated pupil, a peripheral secondary cataract or a peripheral capsule opacification or an anterior capsular phimosis. Therefore, sometimes the separate determination of the axial refraction for the near and the far part is not sufficiently accurate.

The new iTrace device (Tracey Technologies, Houston, Texas, USA) could provide more accurate measurement results. This wavefront device uses significantly smaller cones of light (about 1mm) that should allow you to determine more accurate readings in multifocal optics.

A reliable objective refraction is required if patients fail to achieve sufficient visual acuity after the implantation of a multifocal IOL.

This study will investigate whether the new iTrace device (Tracey Technologies, Houston, Texas, USA) is suitable for precisely measuring the far and near part of the LS-313 MF30 Intraocular Lens.

Comparative devices are the refractometer PR 50 or PR 60 (Rodenstock, Munich), the determination of the subjective refraction and the determination of the refraction with auto-refractometers, which are available at the Department of Ophthalmology Neubrandenburg.

## 2. SYNOPSIS

### 2.1 Study objective

This study protocol is designed to collect postoperative refraction readings follow implantation of a multifocal Intraocular Lens (LS-313 MF30) with the following devices:

- Eye Refractometer PR 60 or PR 50 (Rodenstock, Munich),
- ITrace (Tracey Technologies, Houston, Texas, USA),
- Autorefraktor Mod. ARK-760A (NIDEK CO, LTD, Gamagōri, Japan),
- Autorefraktor Mod. ARK-560A (NIDEK CO, LTD, Gamagōri, Japan),
- Autorefraktor KR-800s (TOPCON, Willich, Germany),
- Combined keratometer and aberrometer KR-1W (TOPCON, Willich, Germany).

The subjective refraction is additionally determined as a reference method.

The purpose is to find an accurate objective method for measuring refraction in patients with multifocal lenses of the type LS-313 MF30.

### 2.2 Study population

- 100 eyes should be included in the study

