#### 2.1.2 Exclusion criteria for patients

- Patients with corneal opacities that interfere with the refraction measurements
- Patients with posterior capsule opacity already developed, which interferes with the refraction measurement, if the patients refuse the removal of the secondary cataract.

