### 3. OBSERVATION PERIOD

The patients participating in the study will be examined once in the Department of Ophthalmology of the Dietrich-Bonhoeffer-Klinikum Neubrandenburg.

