### 4. EXECUTION

#### 4.1 Patient recruitment

Patients who received the multifocal lens LS-313 MF30 in Neubrandenburg at one or both eyes will be asked to participate in this observational study.

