#### 4.4 Documentation

A data collection form (attachment) is used. The following intraoperative information is collected retrospectively from the electronic patient file of the Dietrich-Bonhoeffer-Klinikum:

- Name and address of the patient
- Date of Birth
- Date of surgery
- Surgeon
- Operated eye (OD/OS)
- Performed cataract surgery with or without femtosecond laser
- Refractive power of the MICS IOL

The following postoperative information will be collected prospectively within the examination date, for the respective patient's eyes treated with the LS-313 MF30 Multifocal Lens:

- postoperative objective refraction values using auto-refractors in miosis
- postoperative objective refraction values using the PR 50 and 60 (Rodenstock, Munich)
- postoperative objective refraction values using the KR-1W (TOPCON, Willich, Germany)
- postoperative objective refraction values, pupillometry, topography and aberrometry with the iTrace in miosis and mydriasis (Tracey Technologies, Houston, Texas, USA)
- postoperative subjective refraction values with and without correction for the determination of the far and near vision
- pupil width in miosis and mydriasis
- corneal condition
- Assessment of vision impairment by the anterior capsule
- Centering of the intraocular lens
- IOL axis according to TABO scheme
- Assessment of the clarity of fundus insight

A data collection sheet serves as documentation and will be transferred into the Excel database (version 14.0.7166.5000/32-Bit, Microsoft, USA) by the study assistants.

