## 7. DATA PROTECTION

The identification of the patients participating in the study and the patient-related information will be treated confidentially. The protection of the data of the patient is always guaranteed. All personal data of the patient will be pseudonymised (see above).

The patient data determined during the study are first documented on the data collection form. Each patient is assigned a sequential identification number. The data is transferred to the Excel data table with this identification number. In a separate patient list, which is stored in the study folder, the identification numbers are assigned to the patient. Only the study team has access to this study folder. The study assistant ensures that it is no longer possible to draw any conclusion from the data stored in Excel to the respective patient.

In the case of publication of the study results no personal data may be used. The medical staff responsible for the transfer of the data from the patient record must be informed about their data protection responsibility.

Upon completion of the study, the investigator will be required to archive the identification list and documentation of the data collected in the study for at least 15 years in paper format.

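### Does a target of 100 eyes, with one or both eyes per patient, leave the study size undefined?

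*Protocol*

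**What the plan says.** Section 2.2 states the planned size in a single line: "100 eyes should be included in the study". It gives no number of patients. Section 4.1 says: "Patients who received the multifocal lens LS-313 MF30 in Neubrandenburg at one or both eyes will be asked to participate in this observational study". Section 4.4 has the postoperative data collected "for the respective patient's eyes treated with the LS-313 MF30 Multifocal Lens", and section 3 provides for one visit: "The patients participating in the study will be examined once". There is no limit of one eye per patient and no rule for choosing an eye.

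The criteria in 2.1.2 are headed and worded by patient, for example "Patients with corneal opacities that interfere with the refraction measurements". The second criterion, on posterior capsule opacity, is worded the same way and applies only when the patient declines its removal.

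Section 7 states: "Each patient is assigned a sequential identification number". Section 4.4 lists the operated eye (OD/OS) among the recorded items. Section 5 poses the main question, which method is accurate and reproducible with subjective refraction as reference, and sets no numerical target.

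**The concern.** A patient with the lens in both eyes fills two of the 100 places at one visit. The differences between a device and the subjective reference in those two eyes may be alike, because the same person gives both subjective refractions and the two eyes share features such as pupil size. If so, 100 eyes of 50 people carry less information than 100 eyes of 100 people, and the protocol does not say which it will be. At stake is the precision of each device's bias and limits of agreement. If the pairing were also ignored in the analysis, intervals would be too narrow.

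A separate worry is the unit of exclusion. Read literally, an opacity in one eye removes the clear fellow eye too; read by eye, the clear eye stays. Two members of staff could decide differently. This ambiguity does not create the range of patient numbers, which comes from the eye-based target and the one-or-both-eyes recruitment alone.

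**Working it through.** **The stated figure.** The 100 cannot be re-derived: the protocol gives no alpha, power, SD, margin or precision target. What can be checked is how many patients it allows and what that does to precision.

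**Patients.** Each patient contributes one or two eyes, so patients = 100 − (number of bilateral patients).
- 0 bilateral: 100 patients
- 25 bilateral: 75 patients
- 50 bilateral: 50 patients

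**Precision.** Let f be the share of eyes that come from bilateral patients (0, 0.5 and 1 in these three cases) and ρ the between-eye correlation of the device-minus-reference difference. The document gives neither the mix nor ρ; values of 0.2, 0.5 and 0.8 are assumed. Then, with SD the standard deviation of that difference:
- design effect = 1 + fρ
- effective n = 100 / (1 + fρ)
- 95% half-width for mean bias = 1.96 × √((1 + fρ)/100) SD
- 95% half-width for a limit of agreement = 1.96 × √((1 + fρ)/100 + (1.96²/(2 × 99)) × (1 + fρ²)) SD

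Example, 75 patients and ρ = 0.5: the design effect is 1 + 0.5 × 0.5 = 1.25, effective n is 100/1.25 = 80, and the half-width for bias is 1.96 × √0.0125 = 0.219 SD.

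| Patients | ρ | Effective n | Mean bias (SD) | Limit of agreement (SD) |
|---|---|---|---|---|
| 100 | any | 100 | 0.196 | 0.336 |
| 75 | 0.2 | 91 | 0.206 | 0.344 |
| 75 | 0.5 | 80 | 0.219 | 0.363 |
| 75 | 0.8 | 71 | 0.232 | 0.390 |
| 50 | 0.2 | 83 | 0.215 | 0.352 |
| 50 | 0.5 | 67 | 0.240 | 0.388 |
| 50 | 0.8 | 56 | 0.263 | 0.437 |

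**In dioptres.** Assume an SD of 0.5 D (not in the document).
- Middle case (75 patients, ρ = 0.5): bias interval wider by (0.219 − 0.196) × 0.5 ≈ 0.01 D on each side; limit of agreement by (0.363 − 0.336) × 0.5 ≈ 0.01 D.
- Extreme case (50 patients, ρ = 0.8): (0.263 − 0.196) × 0.5 ≈ 0.03 D and (0.437 − 0.336) × 0.5 ≈ 0.05 D.

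**Is the second eye worth having?** With 50 patients and one eye each, the half-width for bias is 1.96/√50 = 0.277 SD. With both eyes of the same 50 patients it is 0.240 SD at ρ = 0.5 and 0.263 SD at ρ = 0.8. The fellow eye adds information for any ρ below 1.

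**Unit of exclusion.** Both opacity criteria turn on whether the opacity interferes with the refraction measurement, and every measurement in section 4.5 is made on one eye at a time. Under either reading, an eye with an interfering opacity is left out and the included eyes are measurable. The readings differ only in whether some clear fellow eyes are used. Because the target counts eyes, any that are dropped would be made up by further recruitment.

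**The case for a change.** The strongest case for a change is that the number of people and the unit of exclusion are settled at recruitment. An analysis can allow for clustering, but it cannot supply independent patients who were never enrolled. A line in 2.2 and a word in 2.1.2 would cost almost nothing and would tell readers what 100 eyes is worth. The reasoning about recruitment is correct, and the extra words would do no harm.

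The case falls short in three ways. First, no mix of patients makes the study miss anything it promises, because no precision or power is promised. Second, the one measure that would alter the amount of information is a cap on bilateral patients, for instance at least 75 patients with at most 25 counted twice. Such a cap has no basis in the document. It could require up to 25 more people than an all-bilateral sample, with their visits and insurance, and would discard fellow eyes that section 4.4 has measured anyway. Third, stating the expected mix or the unit of exclusion records detail without altering what a sensible team would do.

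The risk of intervals that are too narrow is real only if the pairing is ignored. In that event, nominal 95% coverage for mean bias would be 92.0% with 75 patients at ρ = 0.5, and 85.6% with 50 patients at ρ = 0.8. Nothing in the protocol proposes such an analysis. Comparisons between devices deserve the same care: error in the shared reference cancels, but device differences may still be correlated between fellow eyes.

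**Conclusion.** No change follows. The range of 50 to 100 patients is real, and so is the patient-level wording of eye-level exclusions. Counting measurement units in eyes while consenting people is normal in a study of this kind, and using both eyes of a bilateral patient is a fair trade-off. Over the assumed range, the half-width for a device's mean bias lies between 0.196 and 0.263 SD and that for a limit of agreement between 0.336 and 0.437 SD. The upper ends need every patient to be bilateral and a correlation of 0.8. Handling of paired eyes is commonly left to an analysis plan, which is not shown, and the patient number and operated eye already recorded are enough for an analysis with the patient as cluster. The exclusion wording is a gap that the team can fill sensibly, and the plan gives sound results under either reading.

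This conclusion rests on the assumed correlations and bilateral shares, and on the pairing being respected when intervals are computed.

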#### 2.1.1 Inclusion criteria for patients

- Patients after cataract surgery with implantation of the MICS-IOL LS-313 MF30 and complete postoperative corneal clearing
- At least 18 years of age
- Signed consent form

#### 2.1.2 Exclusion criteria for patients

- Patients with corneal opacities that interfere with the refraction measurements
- Patients with posterior capsule opacity already developed, which interferes with the refraction measurement, if the patients refuse the removal of the secondary cataract.

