## 8. SAFETY

The risk of an adverse event is low in this study because only measurements are taken on different devices and no eye surgery is performed.

Adverse events related to the necessary investigations that are to be expected are listed here:

- in Mydriasis (dilation of the pupil)
  - glare sensitivity
  - allergic reaction
  - continuous dilation over 2 to 3 days
- Accident on the way to the investigations

To safeguard the patients, study and travel insurance are taken out.

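### Does the exclusion rule on posterior capsule opacity bring eye surgery into a study described as measurement only?

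*Protocol*

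**What the plan says.** Section 2.1.2 of the Protocol has two exclusion criteria. The second concerns "Patients with posterior capsule opacity already developed, which interferes with the refraction measurement, if the patients refuse the removal of the secondary cataract". Its effect depends on the patient's answer: refusal excludes, and acceptance, by implication, does not.

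Three other sections describe what the study does:

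- Section 3: "The patients participating in the study will be examined once in the Department of Ophthalmology".
- Section 4.1: patients who received the lens at this hospital "will be asked to participate in this observational study".
- Section 8: the risk is low "because only measurements are taken on different devices and no eye surgery is performed". A list follows, introduced by "Adverse events related to the necessary investigations that are to be expected are listed here". It contains effects of pupil dilation and an accident on the way to the examination.

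Section 1 gives the dimensions that matter for the side question. The PR 50 and PR 60 refractometers "work with light cones of 3 mm diameter", and the lens optic "has a diameter of 6 mm, half of the optic is used for far vision, half for near vision". It also says that the PR beam usually cannot be imaged in full "in case of a non-maximally dilated pupil, a peripheral secondary cataract or a peripheral capsule opacification or an anterior capsular phimosis".

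**The concern.** A rule that turns on refusal presupposes an offer. The trigger is interference with the study's own measurement and not a clinical indication, and the corneal-opacity criterion beside it has no comparable clause. Removal can therefore look like a route into the study. Read that way, three things seem to go wrong.

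1. The reason given in section 8 for low risk would not hold for patients treated in order to enter, and the list of expected events would not cover them.
2. The lens is checked at the slit lamp (4.5.14), the last investigation listed. An opacity first recognised there could not be removed and the eye then measured again within a single examination.
3. Eyes measured after removal would be pooled with eyes whose capsule was always clear, and section 4.4 has no dedicated item to separate them.

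There is also a side question. Six device types and a subjective reference are used, but the criterion does not say which method the opacity must disturb. If disturbance of the PR refractometer alone counted, some eyes with peripheral opacity could be left out or measured only after removal. Those are eyes in which section 1 expects the iTrace, with its narrower beam, to do better.

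**Working it through.** The main point involves no stated figure, so the check sets the sections side by side under the two possible readings.

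**Reading A: removal is care given before and outside the study.**
- Section 2.1.2 only filters patients. It does not schedule, order or pay for removal.
- Section 8 speaks of risk in this study and of events from its necessary investigations. Sections 4.5.1 to 4.5.14 list those investigations, and removal is not one of them, so its absence from the event list is consistent.
- Section 3 counts examinations of participating patients. A patient still deciding on removal need not yet be one.
- The observational label in section 4.1 is unaffected.
- Result: no conflict.

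**Reading B: removal is done in order to enter the study.**
- The reason in section 8 fails for those patients and the event list does not cover them.
- The single examination becomes a problem only if, in addition, the opacity is first found at that examination. Participants received their lens at this hospital (4.1) and their records are used (4.4, 4.5.1), so it may be known earlier.
- Result: a conflict. But no section states reading B; it has to be inferred.

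**Effect on the results.** Section 4.4 plans the device readings and the subjective refraction in each study eye, so methods are compared within the eye. An earlier removal precedes all of them. Nothing in the protocol shows that it would shift one method against another. Past operations (4.5.1), lens translucency and any abnormality (4.5.14) and fundus clarity (4.4) are recorded.

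**Side question: how much of each beam would a peripheral opacity block?**

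Inputs: optic radius 3 mm and PR cone diameter 3 mm (section 1); iTrace pattern diameter 1 mm, centred 1.5 mm from the lens centre (4.5.12).

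Assumptions: opacity concentric with the lens, all lengths in one plane, PR cone a full disc filling one half of the optic (radius 1.5 mm, centre 1.5 mm out).

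The iTrace pattern spans 1.5 − 0.5 = 1.0 mm to 1.5 + 0.5 = 2.0 mm from the centre. It is untouched while the clear zone has a diameter of at least 2 × 2.0 = 4.0 mm.

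Share blocked = 1 − (overlap of measuring circle and clear circle) / (area of measuring circle), with the overlap from the two-circle formula:

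| Clear diameter (mm) | PR blocked | iTrace blocked |
|---|---|---|
| 6.0 | 0% | 0% |
| 5.5 | 5.5% | 0% |
| 5.0 | 14.8% | 0% |
| 4.5 | 25.8% | 0% |
| 4.0 | 37.6% | 0% |
| 3.5 | 49.4% | 21.8% |

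On these assumptions, clear zones from 4.0 mm to just under 6.0 mm disturb only the PR reading.

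Section 4.5.11, however, describes an annular illumination zone and gives no inner radius. With assumed inner radii of 0.5, 1.0 and 1.25 mm, a 4.0 mm clear zone blocks 42.3%, 48.6% and 51.1% of the ring instead of 37.6%. Section 4.5.11 tolerates a zone that lies mostly within the pupil. Whether such an eye still counts as measurable by PR therefore depends on a dimension the protocol does not give.

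**The case for a change.** The strongest case for a change is that eligibility, procedures and risk belong in the protocol and cannot be left to an analysis plan. The benign reading is nowhere written down, and an ethics committee (section 6) or insurer (section 4.2) cannot tell from the text which reading applies. One sentence would settle it.

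Part of this stands. Section 2.1.2 does not say when or under whose responsibility removal takes place. If it were done in order to enter the study, sections 2.1.2, 3, 4.1 and 8 would have to be reconciled. But that is a condition and not something the documents state.

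The point about data is weaker. The data collection form named in section 4.4 is an attachment that is not shown, so a missing field cannot be asserted. Items already listed give prior removal and media clarity a place.

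The side question does not carry weight either. The geometry is correct on its assumptions, but no section bases eligibility on a failed device reading, and corrected acuity (4.5.3) is listed before any device. Choosing one method as the test would also help decide whose acceptance or refusal of removal counts. That is a clinical rule, which this review leaves alone.

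**Conclusion.** No change to the plan follows. The apparent contradiction is conditional: it exists only if removal of a secondary cataract is performed as a step of the study, and no section says so. On the other reading, which suits an exclusion criterion and the list of investigations, sections 2.1.2, 3, 4.1 and 8 agree.

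For the analysis, the comparison is within the eye and follows any earlier removal, so no wrong estimate or conclusion has been shown. The number of eyes concerned cannot be estimated from the protocol. The beam figures (up to 37.6% of the PR disc blocked at a 4.0 mm clear zone, or 42.3% to 51.1% for the assumed rings, against 0% for the iTrace) describe the optics. They do not show that eyes are selected in favour of one device.

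What remains is an unstated detail about the timing and status of removal, which the study team can fill sensibly. This conclusion assumes that removal is not carried out for the purpose of the study and that it comes before all study measurements in the eye. It takes no position on whether or when removal should be done.

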### 2.3 Study design

- prospective, monocentric study

### 2.4 Study investigation plan

- a prospective postoperative examination at the Department of Ophthalmology Neubrandenburg
- retrospective collection of surgical data from the medical record of the Department of Ophthalmology at the Dietrich-Bonhoeffer-Klinikum, Neubrandenburg

### 3. OBSERVATION PERIOD

The patients participating in the study will be examined once in the Department of Ophthalmology of the Dietrich-Bonhoeffer-Klinikum Neubrandenburg.

